US IMAGING						
US-score PsA-SIR		X		X	X	X
CR IMAGING						
X ray (hands-feet)		X			X	X
ADVERSE EVENTS			X	X	X	X

STATISTICAL ANALYSIS PLAN

VARIABLES: OUTCOME MEASURES

PRIMARY:

- MDA at 6 months

SECONDARY

- MDA at 12 months, sustained MDA at 6 AND 12 months
- DAPSA <3.3 at 6 months, 12 months, 6 AND 12 months
- Δ mSvH 0-12 and 0-24 months
- Δ HAQ 0-12 and 0-24 months
- Δ PSAID 0-12 and 0-24 months
- US-score PsA-SIR damage subscore at 0-6-12 months

US PREDICTORS

- US-score PsA-SIR
- US-score PsA-SIR inflammation subscore
- US-score PsA-SIR damage subscore

CLINICAL PREDICTORS

Based on the relevant literature clinical variables to be considered in the model include:

- Demographic and environmental factors:
 - Age
 - Gender
 - Smoking
 - BMI
- Clinical factors:
 - subset of PsA
 - time from symptoms onset to diagnosis
 - disease duration
 - disease activity (DAPSA and BASDAI)
 - HAQ score
 - tender joints / pain
 - comorbidities (FM, MetS)
- Serological factors:
 - Acute phase reactants
- Therapy factors:
 - Treatment (NSAIDs, steroids, DMARDs)

DESCRIPTIVE ANALYSES

Descriptive data will be provided for all outcomes according to data type; number of patients (N), mean, standard deviation (for interval data), median 25% and 75% quartiles (for ordinal data). Frequency (absolute and relative) distributions will be provided for categorical data. Two-sided p-values will be presented throughout.

PRIMARY ENDPOINT ANALYSIS

Prediction of 6 months MDA will use multivariate adjusted logistic models. A baseline model will include all the clinical variables. US predictors will be added as covariates to the clinical variables, assuming an additive model. The derived β coefficients were used to calculate prognostic indices, thereby creating weighted prediction models.

Model performance will be evaluated by C-indices (area under the ROC curve, AUC), net reclassification indices (NRI), integrated discrimination improvement (IDI), and plotted ROC curves. NRI can be used to compare the clinical impact of different models (it is a comparison of the proportion of subjects with disease who have appropriately increased risk scores with the new model, and the proportion of subjects without disease who have appropriately decreased risk scores with the new model). IDI represents desired improvements in average sensitivity corrected for undesirable increases in 1-specificity, it therefore compared whether the new models improved sensitivity without affecting specificity.⁽³⁰⁾

Data management and analysis will be performed using RedCap, R, Stata.

SECONDARY ENDPOINT ANALYSES

- to evaluate the additional value of US over clinical examination in detecting patients:
 - achieving MDA at 12 months
 - achieving sustained DAPSA remission at 6 and 12-months
 - achieving DAPSA remission at 6 and 12 months
 - achieving ACR Remission remission at 6 and 12 months
 - with X-ray structural progression (mSVH score) at 12 and 24 months
 - with US structural progression (US-damage score) at 12 and 24 months
 - with functional worsening (Δ HAQ>0.23) at 12 and 24 months
 - with impairment of HRQoL at 12 and 24 months

The same approach followed for the primary endpoint will be followed to evaluate

EXPLORATORY ANALYSES

- to evaluate the relationship between time-integrated US-detected inflammation and US-detected erosions at 12 and 24 months
- to evaluate the comparative effectiveness of different treatment strategies on MDA, DAPSA remission, Δ HAQ>0.23, X-ray progression (mSvHS), US-inflammation score, US-damage score.
- to evaluate the comparative effectiveness of different treatment strategies on MDA, DAPSA remission, Δ HAQ>0.23, , X-ray progression (mSvHS), US-inflammation score, US-damage score.

SAMPLE SIZE

The sample size calculation was done with the objective of minimizing the number of false positives (i.e the number of false non-responsive to treatment) in order to minimize the risk of over-treating patients who actually have a good response to therapy. Therefore, sample size was calculated to minimize this risk by 40% (null hypothesis H0) to 20% (alternative hypothesis H1), maintaining stable at 70% (both for the H0 for both the H1), the percentage of true positives (true unresponsive to therapy).

The simulations were carried out using the procedure `rocsz` Stata (by M. Pepe)³⁰, which allows to determine the power to detect an improvement in the ROC curve. The procedure requires the specification of the percentage of false positive and true positive both for the null hypothesis is for the alternative hypothesis and the percentage of positive / diseased.

Using the command `rocsz 0.7 0.2, na (150) ndb (100) tnull (0.7) fnull (0.4)` of Stata, 250 patients are sufficient to evaluate the performance of a model (and its ROC curve) with 90% power and 5% alpha. Specifically, we have assumed a 70% and a 20% of subjects true positives and false positives, respectively, according to the alternative hypothesis, a 70% and a 40% of subjects true positives and false positives, respectively, according to the null hypothesis, and a percentage of diseased of 60% (150 of 250 subjects).

Under the assumption of maximum attrition of 20%, the sample size will be increased to 300 patients. The same sample size is sufficient to precisely estimate a logistic model of achievement of a MDA (probability of 0.4 at 6 months) with 10 predictors (rule of thumbs).⁽³¹⁾

Based on the pre-study activities, 35-40 centres will be involved, 15 tertiary and 20-25 secondary rheumatology centres. Assuming 4 eligible patients/months for tertiary and 1/month in secondary centres, a 40% of enrolment rate, about 30 patients/months are expected.

ETHICS

This study will be conducted in accordance with all applicable laws and regulations including, but not limited to, the International Conference on Harmonisation (ICH) Guideline for Good Clinical Practice (GCP), EU guidelines and the ethical principles that have their origins in the Declaration of Helsinki. The institutional review board (IRB)/independent ethics committee (IEC) must review and approve the protocol and informed consent form before any subjects are enrolled. Before any protocol-required procedures are performed, the subject must sign and date the IRB/IEC-approved informed consent form.

Clinical data (including AEs and concomitant medications) will be entered into a validated data capture system provided by the Italian Society for Rheumatology. The data system will include password protection and internal quality checks, such as automatic range checks, to identify data that appear inconsistent, incomplete, or inaccurate.

PUBLICATION RULES

The study protocol will be submitted for publication and all the results of all the analyses stored at the <https://osf.io/f8mrg>.

Following completion of the study, the full results of this research will be published in a peer reviewed scientific journal. An Open Access publication policy will be applied.

As this is a multi-centre study, the results from individual centres must not be published prior to the publication of the entire study results and without prior agreement of the Steering Committee. For avoidance of doubt the first publication must be the responsibility of the Chief Investigators. A main authorship will be offered to all Local investigators who achieve the minimum target of 20 patients with complete clinical and ultrasound data at baseline and >80% of complete data at 6 months. All the other Investigators not reaching these criteria will be included in the collaborator's list or in the acknowledgements according to the table below.

Number of patients	Sonographer	Clinician
20	Author	Author
10-19	Author	Collaborator
5-9	Collaborator	Acknowledgment
<5	Acknowledgment	

All the investigators will be able to apply to investigator-initiated-studies using the entire data-set, being able to define the authorship according to International Committee of Medical Journal Editors Recommendations.⁽³²⁾

-
- ¹ Moll JM, Wright V. Psoriatic arthritis. *Semin Arthritis Rheum*. 1973;3(1):55–78
- ² Coates LC, Helliwell PS. Validation of minimal disease activity criteria for psoriatic arthritis using interventional trial data. *Arthritis Care Res*. 2010 Jul 1;62(7):965–9
- ³ Gossec L, Smolen JS, Ramiro S, Wit M de, Cutolo M, Dougados M, et al. European League Against Rheumatism (EULAR) recommendations for the management of psoriatic arthritis with pharmacological therapies: 2015 update. *Ann Rheum Dis*. 2015 Dec 7;annrheumdis – 2015–208337
- ⁴ Sokoll KB, Helliwell PS. Comparison of disability and quality of life in rheumatoid and psoriatic arthritis. *J Rheumatol*. 2001 Aug;28(8):1842–6
- ⁵ Eder L, Thavaneswaran A, Chandran V, Cook RJ, Gladman DD. Obesity is associated with a lower probability of achieving sustained minimal disease activity state among patients with psoriatic arthritis. *Ann Rheum Dis*. 2015 May;74(5):813–7

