 - achieving DAPSA remission at 6 and 12-months (including sustained)
 - achieving ACR remission at 6 and 12 months (including sustained)
 - with X-ray structural progression (mSVH score) at 12 and 24 months
 - with US structural progression (US-damage score) at 12 and 24 months
 - with functional worsening (Δ HAQ>0.23) at 12 and 24 months
 - with impairment of Health Related Quality of Life (HRQoL) at 12 and 24 months;
- to evaluate the relationship between time-integrated US-detected inflammation and US-detected damage at 12 and 24 months;
- to evaluate the comparative effectiveness of different treatment strategies on MDA, DAPSA remission, Δ HAQ>0.23, X-ray progression (mSvHS), US-inflammation score, US-damage score;
- to evaluate residual US activity in patients in MDA remission;
- to explore whether clinically-detected disease activity due to joint tenderness without swelling is related to joint or extra-articular US-detected inflammation evaluated by US;
- to explore clinical features and US-lesions related to X-ray detected bony apposition.

STUDY DESIGN

The study follows a multi-centre observational prospective cohort study design.

The study is registered at Open Science Framework.⁽¹⁶⁾

PARTICIPANTS

CENTRE SELECTION

All the members of the Italian Society of Rheumatology will be invited to participate to the UPSTREAM Study. In order to increase the validity and reliability of the results, the participants will be selected based on three prerequisites:

- local availability of a high level US machine including high level US probes (>14MHz);
- reliability exercise on static images with a kappa statistics value >0.7 compared with a 'gold standard' scorer;
- quality assessment of US images of PsA lesions.

PATIENT SELECTION

INCLUSION CRITERIA

- Adult > 18 years of age with PsA (according to the CASPAR classification Criteria)
- Clinically active arthritis, with at least one joint clinically involved (both swelling and tenderness) in patient not achieving the MDA;
- Subject newly prescribed NSAIDs (monotherapy), steroid intra-articular injections (monotherapy), cDMARD, bDMARDs as indicated by the treating rheumatologist according to usual clinical practice before US acquisition;
- Stable treatment before treatment modification (6 weeks);
- Signed informed consent form;

STUDY PROCEDURES

RELIABILITY EXERCISE

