A total of 30 static images per US-lesion type (synovitis, enthesitis, tenosynovitis, erosion, bony apposition) with 50% of presence of lesions will be submitted to scoring through an on-line electronic platform. A reference atlas will be provided to the investigators before the exercise. A second exercise could be offered to investigators who did not achieve a minimum level of kappa after further training at one of the Centres of the PIs.

SCREENING VISIT

The aim of this visit is to identify a patient who might be suitable for inclusion in the study.

- Consent: Inform the patient about the nature and objectives of the study and obtain his/her written informed consent;
- Check inclusion/exclusion criteria;
- Check cumulatively CASPAR criteria since the onset of PsA;
- Assign patient number (PN) in sequential order, if the patient is suitable for the inclusion in the study.

BASELINE VISIT

The aim of this visit is to confirm that the patient is appropriate for inclusion in the study, determine disease activity state, undertake a complete high resolution ultrasound assessment and X-ray of hands and feet. If a X-ray has been already done within the 6 months before the study entry is not requested to perform a further scanning.

- Record in Case Report Form:
 1. demographic and life-style variables (*smoking, alcohol consumption, BMI*);
 2. drug history (*including past adverse events*);
 3. typical comorbidities associated to PsA (*obesity, diabetes, hypertension, metabolic syndrome non-alcoholic fatty liver disease, IBD, uveitis, anxiety/depression*) and other comorbidities (*e.g. neoplasms, cardiovascular disease, Charlson comorbidity index*);
 4. onset of symptoms and disease duration;
 5. define clinical subset of PsA;
 6. CPR (mg/dl), ESR;
 7. RF, ACPA and HLA B27 (if available);
 8. treatment to be started;
- Procedures for psoriatic arthritis:
 1. Swollen (68) and Tender (66) Joints Count;
 2. Enthesal assessment;
 3. Tender Dactylitis Count;

- Procedures for psoriasis:
 1. Body Surface Area (BSA);
- Questionnaires:
 1. Physician completes VAS Physician global assessment of disease activity (joint and skin) 0-100;
 2. Patients completes pain VAS (0-100), global VAS (0-100), HAQ, BASDAI, PSAID12;
- US assessment:
 1. US-score PsA-SIR;
- X-ray assessment of hands and feet:
 1. Posterior-anterior radiographic assessments of hands and feet (electronic format)

3RD MONTH VISIT

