If in addition to an abnormal peritendinous (ie, intra-sheath) signal there was an abnormal intratendinous signal seen in two perpendicular planes (ie, excluding intratendinous small isolated signals that can correspond to normal feeding vessels detectable by US), then grades 1 and 2 would be increased by one point ⁽²⁸⁾.

Tendon damage can be defined on B-mode as internal and/or peripheral focal tendon defect (ie, absence of fibers) in the region enclosed by tendon sheath, seen in two perpendicular planes. The grade of tendon damage should be assessed in both longitudinal and transverse planes. ⁽²⁹⁾

The overall PsA-SIR US score will be calculated as the sum of the scores of every lesion at all sites (range 0-632).

The inflammatory PsA-SIR US subscore will be calculated as the sum of the scores of GS-sinovitis, PD-sinovitis, GS-tenosynovitis, PD-tenosynovitis, GS-peritenotitis, PD-pertitenonitis, enthesal hypoechogenicity, enthesal thickness, enthesal PD, GS-bursitis and PD-bursitis at all sites (range 0-470).

The damage PsA-SIR US subscore will be calculated as the sum of the scores of joint erosion, bony proliferation, tendon lesion, enthesophytes, enthesal calcifications, enthesal erosions, at all sites (range 0-162).

RADIOGRAPHIC ASSESSMENT

Posterior-anterior radiographic assessments of hands and feet will be scored at a subsequent time point by two radiologists centrally using the van der Heijde modification of the Sharp score. The scoring will be performed pairwise, blinded to the sequence of the films and to the clinical data. Mean of two investigators will be taken as the final score for X-ray assessments.

STUDY VISIT/SCHEDULE

Study Period:	Enrollment	Observation/Follow-up MONTHS				
Visit	Screening	Baseline	3	6	12	24
Informed Consent	X					
Inclusion/Exclusion Criteria	X					
Socio-demographic data		X				
Life-style questionnaire		X				
Medical History		X				
Information treatment		X	X	X	X	X
ARTICULAR ASSESSMENT						
Tender (68) and swollen (66) joint count		X	X	X	X	X
Entheseal assessment		X	X	X	X	X
Tender Dactylitis Count		X	X	X	X	X
SKIN ASSESSMENT						
Body Surface Area (BSA)		X	X	X	X	X
BLOOD TEST						
RF/ACPA/HLA-B27		X				
ESR/CRP		X		X	X	X
PATIENT GLOBAL AND PAIN ASSESSMENT						
Pain VAS		X	X	X	X	X
Global VAS		X	X	X	X	X
PHYSICIAN'S GLOBAL ASSESSMENT						
Physician's Global VAS		X		X	X	X
PATIENT SPINAL ASSESSMENT						
BASDAI		X				
PHYSICAL FUNCTION						
HAQ		X	X	X	X	X
HEALTH-RELATED QUALITY OF LIFE						
PsAID-12		X		X	X	X

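### A baseline X-ray may be up to 6 months old at entry, yet mSvH change is labelled 0-12 and 0-24 months with no film date or interval term, so pre-entry damage counts as on-study progression in the secondary X-ray analyses

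*Combined protocol and SAP*

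**What the plan says.** All references are to the combined protocol and SAP.

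- **Baseline film.** Study Procedures, Baseline Visit, lists hand and feet radiographs but waives a new one where a recent film exists: "If a X-ray has been already done within the 6 months before the study entry is not requested to perform a further scanning".
- **Outcome.** The secondary outcome measures in the SAP include "Δ mSvH 0-12 and 0-24 months". The secondary objectives and the Secondary Endpoint Analyses ask whether ultrasound (US) adds to clinical examination in detecting patients "with X-ray structural progression (mSVH score) at 12 and 24 months".
- **Method.** For all secondary endpoints the SAP says "The same approach followed for the primary endpoint will be followed to evaluate", and the sentence stops there. The primary approach is a clinical logistic model, then the same model with US predictors added, compared by AUC, NRI and IDI.
- **Covariates.** The list that opens "Based on the relevant literature clinical variables to be considered in the model include" covers demographic, clinical, serological and therapy factors. Neither film age nor film-to-film interval is in it.
- **Reading.** Under Radiographic Assessment, "The scoring will be performed pairwise, blinded to the sequence of the films and to the clinical data". This governs scoring and makes no use of film dates.
- **Second use.** X-ray progression is also an outcome in the Exploratory Analyses: "to evaluate the comparative effectiveness of different treatment strategies on MDA, DAPSA remission, Δ HAQ>0.23, X-ray progression (mSvHS), US-inflammation score, US-damage score".

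The baseline case report form items do not include the film date, and no section mentions the actual interval between films.

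**The concern.** A patient filmed at entry and a patient whose baseline film is six months old both contribute a change labelled 0-12 months. The second patient has had half as long again to accrue damage, and all of the extra time precedes the study. Three consequences follow.

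1. **Prediction.** Under Ultrasonographic Assessment, US is done on the day of clinical assessment. It can therefore follow the baseline film by up to six months, and a baseline predictor is then partly tested against damage that had occurred before it was measured.
2. **Treatment comparison.** Damage from before the new treatment is credited to it. The inclusion criteria require stable treatment for only 6 weeks, so an older film may also predate an earlier treatment change.
3. **Selection.** Having a recent routine film is unlikely to be random. If it goes with severity, centre or treatment choice, film age can be associated with US score or with treatment group, and unequal intervals then bias the comparison as well as adding noise.

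**Working it through.** The documents give no progression rate, SD, progressor cut-off or sample size for mSvH, so there is no figure of the plan's own to reproduce. Step 1 needs only the protocol's numbers, with follow-up films on their nominal dates and entry taken as baseline. Steps 2 to 5 rest on stated assumptions.

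**1. Interval.** Let L be the age of the baseline film at entry, 0 to 6 months. The film-to-film interval is 12 + L or 24 + L. The excess over the label is L/12 or L/24. The share falling before entry is L/(12 + L) or L/(24 + L).

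| L (months) | 0-12 label: actual | Excess | Pre-entry share | 0-24 label: actual | Excess | Pre-entry share |
|---|---|---|---|---|---|---|
| 0 | 12 | 0% | 0% | 24 | 0% | 0% |
| 3 | 15 | 25% | 20% | 27 | 12.5% | 11.1% |
| 6 | 18 | 50% | 33.3% | 30 | 25% | 20% |

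**2. Cohort average.** Assume a constant progression rate and film ages uniform over 0-6 months (mean 3). If a share q of patients has an older film, mean change rises by q × 3/12 at 12 months and q × 3/24 at 24 months.

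- q = 25%: about 6% and 3%.
- q = 50%: 12.5% and about 6%.
- q = 100%: 25% and 12.5%.

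If the pre-entry rate is k times the on-study rate, a six-month-old film inflates the 12-month change by k × 6/12. For k from 0.5 to 2 that is 25% to 100%.

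**3. Progressor proportion.** Assume a constant hazard and a true 12-month proportion p. A six-month-old film gives 1 − (1 − p)^(18/12). For p = 10%, 20% and 30% this is 14.6%, 28.4% and 41.4%.

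A simulation gives a smaller gap. Assumptions: gamma-distributed individual rates with mean 0.9 units/year and shape 0.5, reading SD 1 unit, film age uniform over 0-6 months, and progression called at 2 units or more. Fresh films then give about 19.1% progressors at 12 months and older films about 23.2%. With gamma shapes from 0.3 to 2 the ranges are 17.1-19.1% and 21.6-24.1%. At 24 months (shape 0.5) the figures are 33.3% and 35.8%.

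**4. Discrimination.** The objective is judged by AUC, NRI and IDI.

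- *Film age unrelated to the predictor.* In the same simulation, with a predictor correlated with the individual rate, going from no older films to all older films moves the 12-month AUC from 0.699 to 0.703 at a 2-unit cut and from 0.749 to 0.742 at a 3-unit cut. Both changes are below 0.01.
- *Film age related to the predictor.* Take equal numbers with fresh and older films, and a marker with no prognostic value that only tells the two groups apart. Using the step 3 rates, its true-positive rate is 23.2/(23.2 + 19.1) = 0.548 and its false-positive rate is 76.8/(76.8 + 80.9) = 0.487. AUC = 0.5 + (0.548 − 0.487)/2, or about 0.53 instead of 0.50. A simulated null predictor with a looser link to film age reached 0.515. The size depends on the strength of that link, which the documents do not give.

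NRI, IDI and calibration were not simulated.

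**5. Would annualising solve it?** Dividing the change by T years divides the reading error by T as well. At 18 months, an SD of 1 becomes 1/1.5 = 0.67. With the step 3 assumptions, a 2-unit cut on annualised change labels about 17.0% of older-film patients as progressors, against 19.1% with fresh films. The difference reverses; it does not vanish.

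**The case against.** The strongest reply is that this is a permissive feasibility rule on a secondary outcome, that 0-12 is only a visit label, and that no material harm to the study's question has been shown. Much of that stands.

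- A reader might infer that the SAP asserts intervals of exactly 12 and 24 months. It does not; it gives a nominal label and is silent on actual intervals.
- A reader might infer that film timing manufactures progression. It does not. Change between the films, apart from reading error, is real damage; part of it falls outside the labelled window.
- A reader might take 50% and 25% as typical. They apply to a single patient whose film is six months old. The cohort effect scales with a share that the documents do not give.
- The 2- and 3-unit cuts are assumptions. The SAP sets no mSvH progressor cut, which is a more basic gap.
- Added noise alone hardly moves AUC. Material bias needs film age to be related to US score or treatment, and the documents offer no evidence either way.

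The reply does not remove the gap. Patients with different film intervals are pooled under one label, pre-entry change is inside the outcome, and nothing planned would let the analyst see or adjust for either.

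**Conclusion.** The point holds as a gap in the secondary and exploratory X-ray analyses. As written, the plan pools film intervals of 12 to 18 months, and of 24 to 30 months, and counts damage from before baseline US and before the new treatment as on-study progression. The maximum excess is 50% and 25%. The mean among older-film patients is 25% and 12.5%, given uniform film age and a constant rate. The limits of 18 and 30 months are themselves nominal: study entry is not tied to the screening or the baseline visit, and no visit windows are given.

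The illustrated effect is modest: about four percentage points in the 12-month progressor proportion at a 2-unit cut (23.2% − 19.1%), and little change in AUC unless film age is linked to US score. Confidence is high that the gap exists and low about its practical size.

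A reader might infer that the main result is at risk. The documents do not support that, because the primary endpoint is MDA at 6 months and uses no X-ray.

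**What to change.** 1. Record the date of every film. Films are requested in electronic format, so dates for those already taken should be recoverable.
2. In the SAP, add the actual film-to-film interval (or baseline film age) as a covariate in both the clinical and the clinical-plus-US models for X-ray progression, so that US is not credited with what film timing explains. Use the same term in the treatment-strategy comparison.
3. Pre-specify a sensitivity analysis limited to patients whose baseline film was taken close to treatment start, with the window stated in advance. Interval adjustment evens out length but leaves pre-entry change in the outcome; this analysis addresses that part.
4. Report the share of older films and their age by treatment group and by US score.
5. Do not define progressors by a cut on annualised change, for the reason shown in step 5 of the working.

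The cost is one date field per film, one extra model term and a smaller sample in the sensitivity analysis. No additional X-ray is required, and the rule accepting earlier films can stay.
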